5.4 Pharmacokinetic Assessments

Plasma samples are collected at Baseline (0h Pre-dosing) and Day 25 (Confinement) visit (0h Pre-dosing, 1, 2, 3, 4, 5, 6h). The actual values at 0h pre-dose and at 1, 2, 3, 4, 5 and 6h on Day 25 (Confinement) will also be derived and from these the parameters of the parent drug concentration vs time course profile will be determined for each individual patient.

Drug concentrations will be summarised using the designated sampling times (not the actual sampling times) using descriptive statistics (mean, standard deviation, coefficient of variation, median, minimum, maximum, and number of observations) for each treatment group and cohort (Part 1 AD, Part 1 PD, Part 2 PD). However, all PK statistical analyses will be carried out on completion of Part 2. Therefore, the 80mg PD patient data from Part 1 will be included with the PK patient data from the four Part 2 PD patient groups for the PD PK analysis.

PK parameters will be derived using non-compartmental methods (Table 5) using SAS programming. All derivations will be performed using the actual times of blood sampling. All derived parameters (except t_{max}) will also be presented as descriptive summary statistics (mean, SD, minimum and maximum). The time to maximum concentration (t_{max}) will be displayed as median, minimum and maximum.

Table 5: Estimated Pharmacokinetic Parameters - Plasma

Parameter	Description	Calculation
C_{max}	Maximum drug concentration from individual concentration-time curve	Directly obtained from plot
t_{max}	Time to reach maximum concentration	Directly obtained from plot
C_{last}	Last measurable drug concentration	Directly obtained from plot*
T_{last}	Time of the last measurable concentration	Directly obtained from plot*
$\lambda_z (K_{el})$	Terminal-phase rate constant (λ_z) calculated- The value of λ_z from the slope of the regression line of $\ln C$ vs time Assuming - Data points should be randomly distributed around a single straight line; At least 3 data points used in the regression; Correlation coefficient of regression > 0.9000; Period of data points at least 2-fold greater than the calculated half-life Observed terminal elimination half-life	
$t_{1/2}$		$T_{1/2} = \frac{\ln(2)}{\lambda_z}$
AUC_{0-t}	Area under the plasma concentration-time curve from time-zero to the time of the last measurable concentration.	Calculated using the linear trapezoidal rule $((t_2 - t_1) * (C_1 + C_2) / 2)$ during the ascending portion of the curve and the log-trapezoidal rule $((t_2 - t_1) * (C_2 - C_1) / \ln(C_2 / C_1))$ during the descending portion of the curve.
$AUC_{0-\infty}$	Area under the concentration time curve from time-zero extrapolated to infinity	$AUC_{inf} = AUC_{last} + \frac{C_{last}}{\lambda_z}$
CL/F	Apparent systemic clearance	$CL / F = \frac{Dose}{AUC_{inf}}$

*NB: Parameters used in derivations but not presented in data summaries.

For the purpose of calculating AUCs when two consecutive plasma concentrations are below the lower limit of quantification (LLOQ) after t_{max} , all subsequent values will be excluded from derivations. However, single 'embedded' missing values will be included in the derivations with extrapolation between the items.

5.5 Missing Data.

All possible efforts will be made to ensure complete data collection and no imputation of data will be performed.

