3.3 Randomisation

For Part 1: For each cohort (AD, PD) up to 14 subjects will be randomised to posiphen or placebo in a ratio of 10 Active: 4 Placebo.

For Part 2: A sample size of up to 40 Early PD patients will be randomized to one of the 4 posiphen doses, 10 patients each dosed at 5 mg, 10 mg, 20 mg, or 40 mg.

The study is conducted in a blind manner and the randomization schedule for each cohort will be available once all patients in each cohort have completed the required schedule and the data have been locked for that cohort.

4. Population

Three analysis populations are defined for each of the three cohorts (Part 1 AD, Part 1 PD, Part 2 PD):

Intent to treat population

The Intention to treat population (ITT) includes all patients who received at least one dose of study medication and provide post baseline data. Analyses will be based on the treatment actually received and not necessarily that scheduled by the randomisation.

Safety population

The Safety population (Safety) includes all patients who received at least one dose of the study medication. Summaries of safety and tolerability will be based on the actual treatment received.

Pharmacokinetics population

The Pharmacokinetic population (PK) includes all patients who receive at least one dose of study medication and who provide sufficient data to enable parameter estimation.

5. Study Methods

Assessments will be made during three visits (Screening, Baseline and Confinement); in addition there are two telephone calls to assess for adverse events. Specific clinic procedures and details of all assessments performed are given in Section 9 of the protocol.

5.1 Schedule.

Details of all assessments performed with timings are given in Table 2.

Table 2: Clinical Assessments Schedule

Visit Timing	Day -42 to 0		Day 14 (± 4)	1-3 days prior to confinement	Days 25 (± 2)		
Procedures	Screening	Baseline	Phone	Pre- Confinement Phone Contact	Confinement		
					Admission	6-Hour Sampling	Discharge ^e
Informed Consent	X						
Demographics	X						
Medical and Psychiatric History	X						
Height and BMI	X						
Inclusion and Exclusion Criteria	X	X					
Urine Dipstick Pregnancy Test	X						
Physical and Neurological Examination	X	X			X		X
AD & PD: MMSE	X	X			X		
AD: CDR	X	X			X		
AD: ADAS-Cog 14		X			X		
AD & PD: WAIS-IV		X			X		
PD: MDS-UPDRS	X ^g	X			X		
C-SSRS	X	X			X		
Vital Signs ^b	X	X			X	X	X
Clinical Lab Safety Tests	X	X ⁱ			X ⁱ		
12-Lead ECG	X	X			X		X
MRI of Brain ^c	X						

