Adverse Events	X	X	X	X	X	X	X
Prior/Concomitant Medication	X	X	X	X	X	X	X
Randomization		X					
Dispense Study Drug		X					
Dosing Study Drug in Clinic		X					X
Study Drug Compliance Check			X	X	X		
APOE Genotype and DNA Markers		X					
Blood Sampling for PK		X					X
Lumbar Puncture for baseline Pharmacodynamics		X					
LP Catheter Placement ^h					X		
Collecting blood and CSF for Biomarkers in Plasma and CSF		X				X ^f	
24-Hour Phone Follow-Up ^d		X					X
Lumbar Xray ^h (Optional)	X						

^a Refer to Section 9 for more details on visit timing and windows.

^b Vital signs will include sitting blood pressure, pulse, temperature, respiration rate, and weight, except during the 6-hour Sampling Phase of the Confinement Visit when weight will not be included.

^c An MRI of the brain will only be conducted if there is no brain MRI available from within the window specified in Inclusion Criteria.

^d Phone Follow-up should occur approximately 24-hours after completion of the LP procedure at Baseline and after discharge from the Confinement Visit.

^e The Early Discontinuation Visit will contain the same assessments as the Pre-confinement Visit.

^f Sampling Times: 0,1,2,3,4,5,6 hrs (±10 mins for collection)

^g Hoehn & Yahr Stage only for inclusion determination

^h X-Ray is only required if LP insertion will not be performed with fluoroscopy

ⁱ Safety labs at baseline and confinement (for sample 0 hour) should be taken fasted

5.2 Treatment Measures.

Treatment measures are evaluated by pharmacodynamics and by efficacy endpoints.

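### The SAP Table 5 span rule can pass only half-lives up to about 2.0–2.7 h from 6 h of sampling, below every reported mean, and the SAP does not say what happens to a fit that fails

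*SAP*

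**What the plan says.** SAP 5.4, Table 5, derives the terminal rate constant (lambda-z) by regressing log concentration on time. Under the word *Assuming* it lists conditions: at least three points, a correlation above 0.9000, and "Period of data points at least 2-fold greater than the calculated half-life". It does not say whether a fit that misses a condition is dropped, flagged or kept.

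Three parameters in Table 5 use lambda-z: t1/2 is ln 2 divided by it; AUC0-inf ("Area under the concentration time curve from time-zero extrapolated to infinity") adds the last concentration divided by it; and CL/F is dose over AUC0-inf.

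On the schedule, SAP 5.4 states: "Plasma samples are collected at Baseline (0h Pre-dosing) and Day 25 (Confinement) visit (0h Pre-dosing, 1, 2, 3, 4, 5, 6h". SAP Table 2, footnote f, repeats "Sampling Times: 0,1,2,3,4,5,6 hrs" and allows ±10 minutes. SAP 5.4 adds: "All derivations will be performed using the actual times of blood sampling". Protocol 9.4.2 removes the blood line after the 6 h sample.

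Protocol 3.2 gives the peak at 1.2–1.5 h. It gives mean plasma half-lives for 40 and 60 mg of 3.80 ± 0.88 h and 5.23 ± 1.24 h (single dose) and 3.53 ± 1.03 h and 4.104 ± 0.91 h (repeat dosing). It says that half-lives at lower doses could not be determined accurately.

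PK is a primary outcome (Protocol synopsis, Aim 2), and Protocol 2.2 names t1/2 and CL as endpoints. SAP 2.1.4 lists both AUC0-t and AUC0-inf, and SAP 6.4.2 formally tests Cmax and the AUCs for dose proportionality.

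**The concern.** The span rule and the sampling schedule do not fit together at the half-lives the protocol reports. What follows depends on a point the SAP leaves open.

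If failing a condition rejects the fit, t1/2, AUC0-inf and CL/F exist only for patients whose calculated half-life is short. A summary of those values then describes a selected subset and understates the half-life. Reporting the number of observations shows that values are missing. It does not show that they are missing because of the quantity being estimated.

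If the list merely records assumptions, no value is lost, but a large part of AUC0-inf rests on extrapolation from a fit that misses the plan's own standard, and the SAP does not require that part to be shown.

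Either way, two named PK endpoints (t1/2 and CL) and the AUC0-inf version of the dose-proportionality test are affected.

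**Working it through.** The documents state no longest assessable half-life, so there is no planned figure to reproduce.

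**Step 1: the ceiling.** Longest passing half-life = (last fitted time − first fitted time) / 2. With a peak at 1.2–1.5 h, the decline starts between the 1 h and 2 h samples.

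| Fit | Span | Ceiling |
|---|---|---|
| 2–6 h, nominal | 4.00 h | 2.00 h |
| 2–6 h, windows stretched (+20 min) | 4.33 h | 2.17 h |
| 1–6 h, nominal | 5.00 h | 2.50 h |
| 1–6 h, windows stretched (+20 min) | 5.33 h | 2.67 h |

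Even a fit from 0 h through the absorption phase would give 6/2 = 3.0 h (3.17 h stretched), still below 3.53 h. Passing at the reported means needs spans of twice each mean: 7.06, 7.60, 8.21 and 10.46 h. If the rule were read literally as a span three times the half-life, the ceilings would fall to 1.33–1.78 h.

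**Step 2: the share that passes, if failing rejects the fit.** Assume the 40 and 60 mg repeat-dose half-lives apply, are Normal, and ± is an SD. The share is Φ((ceiling − mean)/SD). Example: (2.67 − 3.53)/1.03 = −0.84, so 20.1%.

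| Ceiling | Mean 3.53, SD 1.03 | Mean 4.104, SD 0.91 |
|---|---|---|
| 2.00 h | 6.9% | 1.0% |
| 2.17 h | 9.3% | 1.7% |
| 2.50 h | 15.9% | 3.9% |
| 2.67 h | 20.1% | 5.7% |

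That is about 0.1 to 2 patients in a group of 10. If ± were a standard error with an assumed n of 6–12, 17–40% would pass. Two simulations of the whole rule (correlation and span conditions, actual times within the windows, assay error up to 20%) gave repeat-dose pass rates of 0.5–14% with absorption rate 2 per hour and a free start at 1–4 h, and 0–6% with the peak fixed at 1.35 h and a fixed start.

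**Step 3: the selection.** An accepted half-life cannot exceed the ceiling. It therefore lies at least 1 − 2.67/3.53 = 24% (1 h start) or 1 − 2.17/3.53 = 39% (2 h start) below the lowest reported mean.

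**Step 4: if failing does not reject the fit.** Extrapolated share = (C6/lambda-z) / (AUC0-6 + C6/lambda-z). Assume one compartment, steady state, a 24 h interval and the true lambda-z.

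| Half-life | Absorption 1/h | 2/h | 4/h |
|---|---|---|---|
| 3.53 h | 38.0% | 34.1% | 32.4% |
| 5.23 h | 51.6% | 48.2% | 46.6% |

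**Step 5: doses without a usable half-life.** None is reported for 80 mg, and those at lower doses are described as inaccurate. Purely as a sensitivity check (SD 0.91–1.03 assumed), a mean of 2.0 h would let 50–77% pass over the four ceilings, 2.5 h would let 29–57% pass, and 3.0 h would let 14–37% pass.

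**The case against.** The strongest reply is that the plan foresees gaps. Protocol 2.2 and 6.4 promise PK parameters only as far as the data allow. The PK population needs patients "who provide sufficient data to enable parameter estimation" (SAP 4). SAP 6.4.1 and 7.4 report the number of observations. Rejection is nowhere stated, and Protocol 6.4 makes dose proportionality optional. Cmax and AUC0-t are planned and need no lambda-z, so a proportionality assessment survives. All of this is correct, and it limits the point. It does not cure the selection if fits are dropped, nor the unreported extrapolation if they are kept.

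A reader might infer more than the documents support:

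- *That AUC0-t is already distorted because low-dose profiles end early.* No LLOQ is given, so whether any profile ends early is unknown. A pattern such as last measurable samples at 4 h for 5 mg and 5 h for 10 mg would also conflict with proportional data at the reported half-lives: the 10 mg concentration at 6 h would be 1.35–1.57 times the 5 mg concentration at 4 h, so it would be measurable.
- *That Protocol 3.2 already shows strong non-proportionality.* The figures there are labelled Cmax but carry AUC units, and they cannot support the argument until that is resolved.
- *That the power-model test must always reject.* The equation printed in SAP 6.4.2 uses unlogged dose, but its own sentence and the Figure 1 caption say log dose. This is a slip to correct.

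**Conclusion.** The point holds for the lambda-z rule. The ceiling of 2.0–2.5 h (2.17–2.67 h at the window extremes) is arithmetic from the plan's own schedule, and every reported mean exceeds it.

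The consequences are conditional. If the conditions reject fits and the 40/60 mg repeat-dose half-lives apply with ± read as SD, about 1–20% of patients would have t1/2, AUC0-inf and CL/F, and those values would be selected towards short half-lives. If they do not reject, about 32–52% of AUC0-inf would be extrapolated under the one-compartment assumptions above.

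It would go too far to say that most patients in this trial will lack a half-life: Table 5 does not state rejection, and the share at 5–20 mg and at 80 mg is unknown. Nor does the dose-proportionality analysis fail as a whole, since only its AUC0-inf version depends on lambda-z. The change should be made because PK is a primary outcome and the remedy is cheap.

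**What to change.** 1. **SAP Table 5.** State that failing the span rule flags the fit and does not silently drop it. List t1/2, AUC0-inf and CL/F with the flag and the percentage of AUC0-inf extrapolated, and give the number flagged by dose. Treat these parameters as supportive. Label any summary limited to passing fits as selected towards short half-lives. State that flagged patients stay in the PK population.
2. **SAP 6.4.2.** Base the dose-proportionality conclusion on Cmax and AUC0-t, with AUC0-inf supportive. Report the last measurable time by dose. If it differs by dose, add a sensitivity slope using AUC over the longest interval measurable in all dose groups. Use no imputed values, in keeping with SAP 5.5 ("no imputation of data will be performed"). State that a partial-interval AUC, which here includes AUC0-t, can understate a departure caused by half-life changing with dose. For illustration, suppose half-life rose from 3.53 to 5.23 h over 5–80 mg at constant volume. The full-interval slope would be 1 + ln(5.23/3.53)/ln 16 = 1.14, and the 0–6 h slope about 1.07.
3. **SAP 6.4.2, minor.** Write the model as log(PK) = a + b·log(Dose), with the PK parameter as the dependent variable, and plot against log dose, to agree with the section's own sentence and the Figure 1 caption.

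The cost is SAP and table-shell wording, with no new samples. SAP 6.4 holds all PK analysis until Part 2 is complete, so the change can precede it. The downside is that t1/2 and CL/F, both named endpoints, become supportive.

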6.4 PK Analysis

Plasma concentration-time data will be analyzed by non-compartmental methods using SAS version 9.4 or greater. Calculations will be based on the actual sampling times recorded during the study. Since the study is blinded, all subjects' plasma will be included in the PK analysis. From the plasma concentration-time data, the following PK parameters will minimally be determined, as data permit: Area under the curve (AUC), Cmax, Tmax, t_{1/2}, and CL. Dose-proportionality may be assessed on Cmax and AUC as appropriate. Serial pre-dose trough concentrations Cmax will be assessed for the attainment of steady state.

Plasma concentration-time data for Posiphen will be listed and summarized descriptively (number of subjects (N), mean, median, standard deviation (SD), minimum (min), and maximum (max)) and graphically presented. PK parameters will be listed and summarized descriptively (N, mean, median, SD, min, max, and 95% CI) by each dose regimen. In addition, geometric means and between-subject coefficients of variation (CV) will be calculated.

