7.2 Dosage

The study drug is to be taken orally; one capsule, once a day in the morning, with or without food, for 25 days \pm 2 days at home (depending on when the confinement visit is scheduled).

Participants must take 80% of all doses (across 25 \pm 2 days). Bottles will be examined in clinic at the pre-confinement visit to assess compliance overall and in the last week.

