9.4.2 Confinement Visit

The confinement visit will consist of the following: admission procedures, Time 0 blood and CSF sampling, administration of last dose of study drug, 6-hours of blood and CSF sampling, at least a 1-hour observation period while subject remains on bed rest with the observation period

to be extended as clinically necessary as per the Investigator's decision, and discharge procedures. Subjects will be provided with sleeping accommodations during this visit, if necessary, and maybe permitted to remain overnight per investigator discretion in the event there are adverse events associated with the study medications or study procedures.

Subject confinement visit can be split over two (2) consecutive days should the investigator feel that the neuropsychological tests are better completed one day before the lumbar puncture.

Period 1: Admission

Subjects should arrive fasted in the early morning after an overnight fast. Clinical safety labs will be drawn and sent to the central lab for analysis.

Study drug compliance over the preceding days will be assessed. If there is an insufficient level of drug compliance (less than 80% overall), the site must consult with the Project Directors and Medical Monitor) regarding timing and conduct of the remaining confinement visit procedures. It is possible that subjects will be discontinued early from the study due to insufficient study drug compliance.

Admission visit procedures include conducting a Physical and Neurological Exam, administering functional and cognitive evaluations and C-SSRS, collecting vital signs, ECG, clinical labs, reviewing and recording adverse events and concurrent medications.

Period 2: 6-Hour Sampling

If no medical or compliance concerns are identified during the admission procedures, the subject will move on to the 6-Hour Sampling Phase, which entails the following procedures:

1. Place an intravenous line for blood sampling. Alternatively, blood may be sampled by direct venipuncture if deemed appropriate by the PI.
2. Place the CSF catheter.
3. Collect initial samples of blood and CSF (Hour 0).
4. Administer last dose of assigned study drug after the 0 hour sampling.
 - a. Collect CSF (6 mL) and blood (10mL) every hour at the following time points: 1, 2, 3, 4, 5, 6 hours.
 - i. CSF and blood should be taken within \pm 10 mins of hourly times.

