2.1.4 Pharmacokinetics

PK parameters of the parent drug, posiphen, will be determined for both AD and PD patients at 80mg QD dose group after 25 days of repeated dosing (Part 1) and for PD patients at 5, 10, 20, 40mg QD after 25 days of repeated dosing for PD patients (Part 2).

Specific parameters of interest are Area under the curve (AUC 0-t, 0-inf), maximum concentration (Cmax), time of maximum concentration (Tmax), half-life (t_{1/2}), and clearance (CL).

3. Study Design.

This study will be conducted in two parts: Part 1 will evaluate the safety, tolerability, and pharmacokinetics of Posiphen in 14 Early AD and 14 Early PD patients at 80 mg QD.

Each group will include 14 Early AD patients, randomly assigned, 10 to posiphen and 4 to placebo and 14 Early PD patients randomly assigned, 10 to Posiphen and 4 to placebo.

Part 1 will also include exploratory measures of pharmacodynamics and efficacy of Posiphen with target engagement, pathway engagement and functional/cognitive measures, including the degree of memory loss and cognitive function in AD patients as well as the degree of motor impairment and non-motor symptoms and quality of life in PD patients.

Part 2 will evaluate the safety, tolerability, and pharmacokinetics of posiphen in 40 patients with early PD, who will be randomly assigned to each of 4 dose levels; 5 mg QD, 10 mg QD, 20 mg QD and 40 mg QD.

Part 2 will also include exploratory measures of pharmacodynamics and efficacy of posiphen in Early PD patients with target engagement, pathway engagement and functional/cognitive measures, including the degree of motor impairment as well as other non-motor symptoms and quality of life in PD patients.

Full clinical details are given in the protocol.

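### SAP Table 5's two-half-life rule cannot be met by a 6-hour Day 25 profile, so half-life, AUCinf and CL/F (single-dose formulas on repeated-dose data) would be missing for most patients

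*SAP*

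**What the plan says.** PK is a primary aim (Protocol synopsis and 2.1). Dosing is "one capsule, once a day in the morning" (Protocol 7.2), and SAP 2.1.4 sets the PK assessment "after 25 days of repeated dosing". On the confinement day the site is told to "Administer last dose of assigned study drug after the 0 hour sampling" (Protocol 9.4.2), so the 0 h sample is a trough. SAP 5.4 gives the plasma schedule as "Day 25 (Confinement) visit (0h Pre-dosing, 1, 2, 3, 4, 5, 6h"; nothing is sampled between 6 h and 24 h.

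SAP 2.1.4 lists AUC0-t, AUC0-inf, Cmax, Tmax, half-life and clearance. Table 5 defines AUCinf as AUClast + Clast/λz ("Area under the concentration time curve from time-zero extrapolated to infinity") and CL/F as Dose/AUCinf. It conditions λz on at least three points, a correlation above 0.9, and "Period of data points at least 2-fold greater than the calculated half-life".

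Protocol 6.4 says troughs "will be assessed for the attainment of steady state", but neither document defines an AUC over the 24 h dosing interval. There is no cap on the extrapolated share and no rule for reporting when λz is not accepted. SAP 6.4.2 enters Cmax and AUCs into the formal dose analyses without saying which AUC.

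**The concern.** Two things do not fit together.

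- **Formula and design.** Dose/AUCinf gives apparent clearance after a single dose. After repeated dosing, the area from the last dose to infinity also contains drug left from earlier doses. The matching quantity at steady state is Dose divided by the AUC over one dosing interval.
- **λz rule and sampling window.** A span of two half-lives has to fit between the peak and 6 h. If it does not, half-life, AUCinf and CL/F are not available for that patient.

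At stake are three of the planned PK parameters. With about ten patients per dose group, a dose group might have one or two values or none, from the patients who eliminate the drug fastest. A dose-proportionality analysis of AUCinf would rest on that subset. If the programmer sets the rule aside to fill the table, a large part of each AUCinf comes from time that was never sampled.

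**Working it through.** The plan states no expected extrapolated share, bias or number of evaluable patients, so there is no figure of its own to reproduce.

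**Inputs.**
- Mean plasma t1/2 (Protocol 3.2, 40 and 60 mg): 3.80 ± 0.88 and 5.23 ± 1.24 h after a single dose; 3.53 ± 1.03 and 4.104 ± 0.91 h after repeat dosing.
- Tmax 1.2 to 1.5 h (Protocol 3.2).
- Dosing interval 24 h; samples at 0, 1, 2, 3, 4, 5 and 6 h.
- Assumptions: the unlabelled ± values are SDs; linear one-compartment oral kinetics at steady state; ka solved from Tmax.

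**Step 1. Can the λz rule be met?** Span needed = 2 × t1/2; largest admissible t1/2 = span/2.

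| Mean t1/2 (h) | Span needed (h) |
|---|---|
| 3.53 | 7.1 |
| 3.80 | 7.6 |
| 4.104 | 8.2 |
| 5.23 | 10.5 |

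Time from Tmax to the last sample is 6 − 1.2 = 4.8 h at most. A 2–6 h regression (4 h) admits t1/2 ≤ 2.0 h; a 1–6 h regression (5 h) admits ≤ 2.5 h. Even the whole 0–6 h record would admit only ≤ 3.0 h, below every documented mean.

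**Step 2. How many patients would qualify?** Using the four mean and SD pairs, with normal and lognormal distributions:
- t1/2 ≤ 2.0 h: 0 to 7%.
- t1/2 ≤ 2.5 h: 0 to 16%. For example, (2.5 − 3.53)/1.03 = −1.00 gives 15.9%.

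In a group of ten, the highest figure is 10 × 0.159 = 1.6 patients.

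**Step 3. Extrapolated share if the rule were relaxed.** With k = ln2/t1/2, the share of AUCinf beyond 6 h is exp(−6k) when absorption is ignored: 31% at 3.53 h and 45% at 5.23 h. With absorption included it is 34 to 48%. Running Table 5's own trapezoids and fitted λz on the hourly values gives 35 to 50.5%. For patients who pass the rule at t1/2 of 2.0 to 2.5 h, the share is about 16 to 24%.

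**Step 4. Size of the formula mismatch.** AUC(24 h to ∞)/AUC0-24 = [ka/(ka − k)] × exp(−24k)/(1 − exp(−24k)).
- t1/2 3.53 h: exp(−24k) = 0.0090; the tail adds 1.0%, so CL/F is 1.0% low.
- t1/2 5.23 h, Tmax 1.5 h (ka = 1.91): exp(−24k) = 0.0416; the tail adds 4.7%, so CL/F is 1 − 1/1.047 = 4.5% low.

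Using Table 5's trapezoids as well, the net CL/F error runs from +2.6% to −4.7%.

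**Step 5. Test of the alternative.** Take AUC0-24 with the 0 h trough as the 24 h value and log-linear interpolation from 6 to 24 h. It recovers 96.4 to 97.9% of the true AUC0-24 (CL/F about 2 to 4% high, from coarse sampling round the peak) and needs no λz. About 34 to 47% of the area is interpolated.

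**The case against.** The strongest reply is that the observed metrics survive. Cmax and AUC0-t are already planned, need no λz, and fall within the Cmax and AUCs that SAP 6.4.2 analyses. CL/F is only summarised. Protocol 6.4 derives parameters as data permit, and the SAP's PK population requires data sufficient for estimation, so non-estimable values are partly foreseen. All of that stands, and PK is not lost as a whole. It does not answer the point: the plan names half-life, AUCinf and CL/F as parameters of interest, its own rule excludes them for most patients, and it does not say what is then reported.

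Three stronger readings are tempting but unsupported.
- A reader might infer that CL/F is seriously biased. At the documented half-lives the mismatch is about 1 to 4.5%, and at the repeat-dose half-lives only about 1 to 2%. A figure near 25% arises only with a 12 h half-life, which Protocol 3.2 and 4.2 give for CSF/CNS, in contrast to about 5 h in plasma.
- A reader might infer that clearance would rest mainly on extrapolation. It is about a third to a half if the rule is relaxed, and 16 to 24% in those who pass it.
- A reader might infer that AUC0-24 cures the dependence on unsampled time. Step 5 shows that it does not.

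The trough also has limits. In this model it is about 1 to 6% of the highest hourly value, so it may be unquantifiable at low doses (no assay limit is given), and 80% compliance is accepted, so the previous dose may not have been taken 24 h earlier.

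**Conclusion.** Wrong as written, and correctable in the SAP. The main defect is that Table 5's λz rule and the 6 h window are incompatible at the documented half-lives. The expected result is missing t1/2, AUCinf and CL/F for most patients, with the remainder selected for short half-life. The use of single-dose formulas on a repeated-dose profile is a real mismatch but a minor one numerically.

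The conflict in Step 1 needs only the documented half-lives and sample times. The other sizes are less certain. They assume linear one-compartment kinetics, although Protocol 3.2 reports Cmax rising out of proportion to dose. The half-lives come from 40 and 60 mg; the same section says that those at lower doses could not be calculated accurately. The percentages in Step 2 also depend on reading ± as SD. Table 5 lists the span condition among its assumptions; if it were treated as advisory, the problem would become the uncapped extrapolation in Step 3.

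**What to change.** Amend SAP 2.1.4, Table 5 and 6.4.2 before the PK analysis, which is run only after Part 2.

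1. Define AUC0-24 and CL/F = Dose/AUC0-24 for Day 25. Take the 0 h pre-dose value as the 24 h value, with log-linear interpolation from 6 to 24 h, only where that trough is quantifiable and the previous dose was taken about 24 h earlier. Report the interpolated share per patient (expected about 34 to 47%). State in SAP 5.5 that this is a PK derivation and not an exception to the ban on imputation.
2. Name observed Cmax and AUC over a fixed 0–6 h window as the dose-proportionality metrics. The fixed window replaces AUC0-t where the last measurable sample is earlier than 6 h. Use AUC0-24 as supportive, because troughs may be unquantifiable more often at low doses. Drop AUCinf from that analysis.
3. Report AUCinf and t1/2 only where the λz rule is met, with the number of patients excluded in each dose group.

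The cost is SAP text and programming; no new samples are needed. The downside is that AUC0-24 assumes steady state, which the single on-treatment trough cannot test, and still leans on the unsampled 6 to 24 h period. Its gain is a clearance that matches the design and can be computed without λz, not a smaller numerical error.
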